6.1.6. Suspected unexpected serious adverse reactions

A suspected unexpected serious adverse reaction (SUSAR) is an unexpected adverse drug reaction which also meets the definition of serious adverse events.

6.2. Methods of recording and assessing adverse events

The observation time for AE starts when the treatment is initiated. Participants will be kept for observation for at least 3 hours following each morning treatment for any acute AEs. During the reporting period, any unfavorable changes in the participant's condition will be recorded as adverse events, whether reported by the participant or observed by the investigator. In case of any abnormal finding, the local study physician will perform a full clinical examination and findings will be recorded. An emergency kit will be available on site to treat any medical conditions that warrant urgent medical intervention.

In addition, participants will also be interviewed by a health worker about the occurrence of AEs 24 hours after treatment.

For all AEs, sufficient information will be pursued and/or obtained so as to permit i) an adequate determination of the seriousness of the event (i.e. whether the event should be classified as a SAE); ii) an assessment of the causal relationship between the AE and the study treatments

(i.e. whether the event should be classified as an adverse drug reaction); and iii) an assessment of intensity of AEs by the study physician. Intensity of AE will be judged by the study physician, following guidelines by the European Medicine Agency (Note for Guidance on Clinical Safety Data Management).

All SAE, unexpected adverse drug reactions, or SUSARs must be reported as described in Section 6.3.

6.3. Reporting of serious adverse events

Any study-related unanticipated problem posing risk of harm to participants or others, and any type of serious adverse event including SUSAR, will be reported (within 24 hours after capturing the event and notification) to

[name]. [name] (principal investigator)
Swiss Tropical and Public Health Institute,
[contact]
[contact]
E-mail: [contact]

Within the following 48 hours, the local co-PI must provide to study sponsor-investigator further information on the serious adverse effect or the unanticipated problem in the form of a written narrative. This should include a copy of a completed SAE form, and any other diagnostic information that will assist the understanding of the event. In exceptional circumstances, a SAE may be reported by telephone. In these cases, a written report must be sent immediately thereafter by fax or e-mail. Names, addresses and telephone for serious adverse event reporting will be included in the trial-specific SAE form. Relevant pages from the CRF will be provided in parallel (i.e., medical history, concomitant medications).

6.4. Safety reporting to Health Authorities and Ethics Committees

The sponsor-investigator will send appropriate safety notifications to Health Authorities in accordance with applicable laws and regulations. Additionally, this information will be provided to the 'Ethik Kommission Nordwest- und Zentralschweiz' (EKNZ, Switzerland) and the National Ethic Committee for Health Research (NECHR) according to national rules. Fatal or life-threatening serious adverse events or SUSARs will be reported within 24 hours (between sponsor-investigator's knowledge about the event and notification) followed by a complete

report within seven additional calendar days. Other SAE and SUSARs that are not fatal or life-threatening will be filed as soon as possible but no later than 14 days after first knowledge by the sponsor-investigator.

7. Data management and data quality control

The investigators are responsible for an adequate data quality. Prior to the initiation of the study, an investigators meeting will be held with the investigators and their study coordinators and a member of the Swiss TPH. This meeting will include a detailed discussion of the protocol, performance of study procedures (SOPs), CRF completion, specimen collection and diagnostic methods.

7.1. Source data

Source data are comprised of clinical findings and observations as well as laboratory data maintained and compiled at the study site. Source data are contained in source documents and are allowed to be accessed by local authorities. Source data will be directly entered in the following documents:

1. CRF: Primary data collection instrument for the study. It holds records of all clinical and physical examination data, treatment information and AEs. For every participant enrolled in the clinical trial, a corresponding CRF exists. All data requested on the CRF must be recorded, and investigators will review and approve each CRF for completion.
2. Census: secondary data collected from previously completed census in communities. Holds name, age and sex of each potential participant.
3. Laboratory parasitology sheets: Record of the *Strongyloides* larvae counts and presence of STH eggs at all sample collection time points.

7.2. Data collection and documentation

The data collected and produced from this research project will fall into the following categories:

1. Larvae counts of *Strongyloides stercoralis*, presence of eggs of *Ascaris lumbricoides* and *Trichuris trichiura*, hookworms and *Taenia* ssp. found in participants' stool using either the Baermann technique or standard Kato-Katz microscopy.
2. Personal information such as name, age and gender of trial participants.

3. Baseline and clinical characteristics of the trial participants collected using the study's CRF such as weight, height, blood pressure, temperature, any abnormal medical condition or chronic disease.
4. Number and type of adverse events registered in the CRF and actively probed for 3 and 24 hours after treatment. The same data will further be collected during the collection of the three follow-up periods.
5. Socioeconomic data of each participant's household including behavioural characteristics based on the questionnaire.
6. Genetic profiling of *S. stercoralis* larvae in positive stool samples.

Data from categories 1-4, will be both paper-captured and directly into tablets using CommCare HQ (Dimagi, Inc., Cambridge, MA) or a comparable data-entry software. Data from category 5 will be captured by software only, data from category 6 by paper only. For all data, the software entries will represent the primary data source.

CommCare HQ is a routine data management system ensuring complete, consistent and reliable data entry. For quality assurance error, range and consistency checks will be assessed. 15% of data will be controlled by a standard operating procedure; any discrepancies will be corrected by consulting the hard copy and corrected accordingly. If more than 1% of the double entered data display discrepancies, all data in categories 1-4 will be double entered by two independent people for quality assurance and verified as described.

Data compiled using the software will be directly saved on the personal, password-protected laptop of one of the Co-PIs and uploaded to a server hosted at Swiss TPH, Basel. Data analysis will be conducted with pseudonymized data and reporting of findings will be fully anonymized. In paper-based data collection, all missing data must be explained. All entries will be printed in blue ink. All corrections must be noted with the initials of the respective team member and dated. All categories will be merged into a single master file saved in .xlsx and .csv. Digital copies along with single databases and compiled masterfiles will be transferred to the Swiss TPH, Basel after a Material Transfer Agreement has been signed by both the Swiss TPH and National institute of Cambodia (see Appendix). All data is expected to not exceed 5 GB.

Essential infrastructure such as a locked room for safe storage of hardcopy data will be made available. Digital copies along with the databases will be transferred to the Swiss TPH. Data will then be analyzed as described in section 8.

7.3. Ethical, legal and security issues

Information about study participants will be kept confidential and managed accordingly. Screened participants will be listed in a confidential "participant screening log" and attributed a unique study number. Enrolled participants will be listed in a confidential "participant

enrolment log”; this document will constitute the only source to decode the pseudonymized data and will only be accessible to the investigators. Personal data will be coded for data analysis. No names will be published at any time, and published reports will not allow for identification of single participants. Confidentiality will be ensured throughout the entire research project. All databases will be password secured. None of the investigators declare to have any conflicts of interest.

7.4. Data storage and preservation

All samples will be destroyed after completion of the study. Paper-based and electronic source data and related material will be preserved for a minimum of 15 years to enable understanding of the study procedures, which allows the work to be assessed retrospectively and repeated if necessary. The study site will retain a copy of the documents to ensure that local collaborators can provide access to the source documents to a monitor, auditor, or regulatory agency. Electronic source documents will be stored on a flash drive and kept at the study site (Phnom Penh, Cambodia). The primary data storage and backup will be in the Swiss TPH shared server and secondary data storage will be on personal, password-protected laptops of the PI and co-PI on a password-protected memory stick and/or SWITCHdrive (a cloud storage supported by University of Basel). Electronic data files and archiving conditions will be made strictly confidential by password protection.

7.5. Definition of reference language – translation of study documents

- Protocol: Master document in English and Khmer, all further language versions are translations thereof.
- CRF: Master document in English and Khmer, all further language versions are translations thereof.
- ICF: Master document in English and Khmer, all further language versions are translations thereof.

8. Statistics

8.1. Definition of primary endpoint

Infection status of *S. stercoralis* assessed 14-21 days post-treatment by Baermann's method is the primary outcome.

8.2. Justification of number of trial participants

The main hypothesis of this trial is that an 8 mg dose of moxidectin is non-inferior against *S. stercoralis* compared to the standard of care therapy (ivermectin). We assume a similar true CR for moxidectin and ivermectin of 89% [16]. The sample size determination revealed, that we need 154 participants in each trial arm to demonstrate non-inferiority of moxidectin with a non-inferiority margin of 10%-points with 80 power at the 95% confidence interval (equivalent to the 97.5% lower confidence bound).

To account for an expected loss to follow-up of 10%, we target to enroll $175+175 = 350$ participants.

8.3. Description of statistical methods

An available case analysis (full analysis set according to the intention to treat principle) will be performed, including all participants with any primary endpoint data. Supplementary, a per-protocol analysis will be conducted consisting of all participants who meet all inclusion and exclusion criteria, have no major protocol deviations and received the correct treatment. CRs will be calculated as the percentage of worm-positive adults at baseline who become worm-negative after treatment at the defined follow-up time points. Uncertainty estimates around the differences among CRs will be assessed using melded confidence intervals with mid-p correction as implemented in R's 'exact2x2' package.

LPG will be assessed by calculating the mean of the larvae counts from the Baermann assays (sextuplets for primary endpoint) per gram of stool. The LRR will be calculated ($LRR = (1 - (\text{mean at follow-up}/\text{mean at baseline})) * 100$). Bootstrap resampling method with 5,000 replicates will be used to estimate 95% confidence intervals (CIs) for LRRs and the difference between the LRRs.

Questionnaires on physical functioning and treatment satisfaction will be evaluated by creating summary scores by summing up and transforming the single question scores according to the following formula: $[(\text{actual raw score} - \text{lowest possible raw score}) / (\text{possible raw score range})] * 100$ [47].

AEs will be evaluated descriptively as the difference of proportion reporting adverse events before and after treatment.

9. Duties of the investigator

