4.3.3. Adverse effects assessment

Participants will be kept for 3 hours after treatment administration to observe any possible acute adverse events (AEs) and re-assessment will be done at 24 hours post-treatment. Additionally, interviews will be conducted to determine the emergence of clinical symptoms such as headache, abdominal pain, itching, nausea, vomiting and diarrhea directly before treatment within the scope of baseline assessment. At 3 and 24 hours after treatment and retrospectively at days 14-21, 42-49 and 63-70 days post-treatment, participants will again be interviewed for the assessment of adverse events. Symptoms arising within the time span of 14 days after treatment and the respective follow-up time points will be monitored actively by local health workers who will report incidences to the study team. Any symptoms will be recorded in the case report form (CRF) and immediate action will be pursued if indicated.

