4.6. Schedule of visits

Table 1. Schedule of visits

	Screening / Baseline / Treatment / Safety					Follow-up period		
	Day -90	Day -3 - 0	0 h	1-3 h	24 h	Day 14-21	Day 42-49	Day 63-70
Informed consent	X							
Diagnosis (stool exam) ^(a)	X					X	X	X
Baseline data ^(b)	X							
Questionnaire	X							
Medical history ^(c)		X						
Clinical examination ^(d)		X						
Physical examination ^(e)		X						
Randomization administration of treatment			X					
Capturing AEs ^(f)				X	X	X	X	X
Capturing SAE ^(f)				X	X	X	X	X

^(a) based on duplicate Baermann assays of three stool samples. Daily stool sample will take place in 50-100 adults between day 0 and day 28.

^(b) date of birth, age, sex, height, weight, body temperature, pulse rate, blood pressure, Hb measurement, pregnancy test and recording of breastfeeding.

^(c) information gained by asking specific questions concerning chronic disease and concomitant medications.

^(d) investigation for signs of disease: head ache, abdominal pain, nausea, vomiting, diarrhea, itching, other symptoms.

^(e) physical examination on ear, nose, throat, eyes, lungs, lymph nodes and skin.

^(f) a standardized symptom questionnaire is used, that includes the recording of headache, abdominal pain, itching, nausea, vomiting, diarrhea, allergic reaction, others.

5. Selection of the trial participants

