6.1.1. Types of adverse events

The term “adverse event” is defined as:

Any untoward medical occurrence in participants or clinical investigation subject administered a pharmaceutical product and which does not necessarily have to have a causal relationship with this treatment.

An AE can therefore include any of the following events, which develop or increase in severity during the course of the study, after administration of the study product:

- a) Any unfavorable and unintended sign (including an abnormal laboratory finding, for example), symptom, or disease temporally associated with the use of a medicinal product, whether or not considered related to the medicinal product.
- b) Any abnormality detected during physical examination.

These data will be recorded on the appropriate CRF sections, regardless of whether they are thought to be associated with the study or the drug under investigation. “Associated with the drug” means that there is a reasonable possibility that the event may have been caused by the drug.

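### The before/after AE difference in section 8.3 most plausibly nets resolved baseline symptoms against new ones, so it does not estimate AEs as section 6.1.1 defines them; 'after' is also undefined

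*Combined protocol and SAP*

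**What the plan says.** The statistics section names one AE summary (8.3): "AEs will be evaluated descriptively as the difference of proportion reporting adverse events before and after treatment".

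Elsewhere an AE is confined to the period after dosing:

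- Section 6.1.1 limits AEs to events "which develop or increase in severity during the course of the study, after administration of the study product".
- Section 6.2: "The observation time for AE starts when the treatment is initiated".
- In Table 1 (section 4.6) the AE row is empty up to and including 0 h. It is first marked at 1-3 h, then at 24 h and at the three follow-ups.
- Section 7.2 lists AE data as "Number and type of adverse events registered in the CRF and actively probed for 3 and 24 hours after treatment", and adds the three follow-up periods.

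Symptoms before treatment are nevertheless recorded. Section 4.3.3 plans an interview on "clinical symptoms such as headache, abdominal pain, itching, nausea, vomiting and diarrhea directly before treatment". Footnote (d) of Table 1 describes the clinical examination at Day -3 to 0 as "investigation for signs of disease: head ache, abdominal pain, nausea, vomiting, diarrhea, itching, other symptoms". The Measurements & procedures row of the synopsis counts the pre-treatment interview among the AE interviews.

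After dosing there are five interviews: "At 3 and 24 hours after treatment and retrospectively at days 14-21, 42-49 and 63-70 days post-treatment, participants will again be interviewed".

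The Statistical Analyses row of the synopsis plans AE frequency tables compared descriptively between the treatment groups. Section 8.3 does not repeat this.

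**The concern.** A before/after difference needs a 'before' proportion, and by the protocol's own definition no AE can occur before dosing. The natural stand-in is the pre-treatment symptom record. The difference then becomes a net change in symptom prevalence: a participant whose baseline symptom goes away cancels one who develops a new symptom.

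The symptoms asked about can be present before dosing and gone afterwards. The same number of treatment-emergent events could therefore appear as a rise, no change or a fall, depending on how many baseline symptoms clear. Safety and tolerability of moxidectin is the first secondary objective, so its summary should measure what section 6.1.1 calls an AE.

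A second gap is that one interview directly before dosing is set against five afterwards. Two of these are at 3 and 24 hours, and three look back over weeks. Section 8.3 does not say which one, or which combination, is 'after'.

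**Working it through.** The plan states no AE or symptom rate, so there is no figure of its own to reproduce. All rates below are assumptions; only the arm size of 175 comes from the plan (section 8.2).

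**Definitions**, for the same participants and the same symptom unit at both times:

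- b = proportion symptomatic before treatment
- o = onset among those symptom-free before
- w = proportion of the symptomatic who worsen
- r = proportion of the symptomatic who resolve (w + r ≤ 1)

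**Step 1: the 8.3 figure**, taking both sides as symptom prevalence.

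- Before: b
- After: b(1 - r) + o(1 - b)
- Difference: o(1 - b) - r·b

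The term w does not appear, because someone who worsens reports a symptom both times.

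**Step 2: the 6.1.1 quantity**, new or worse after dosing: o(1 - b) + w·b.

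The two agree only if nothing resolves and nothing worsens.

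**Step 3: numbers**, with o = w = 10%.

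| | b = 30% | b = 10% |
|---|---|---|
| AE per 6.1.1 | 7.0 + 3.0 = 10.0% | 9.0 + 1.0 = 10.0% |
| 8.3 figure, r = 0% | 7.0 - 0.0 = +7.0 | 9.0 - 0.0 = +9.0 |
| 8.3 figure, r = 25% | 7.0 - 7.5 = -0.5 | 9.0 - 2.5 = +6.5 |
| 8.3 figure, r = 50% | 7.0 - 15.0 = -8.0 | 9.0 - 5.0 = +4.0 |

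In every cell 10% of the arm (17.5 of 175) has an AE as defined. With b = 30% the 8.3 figure crosses zero at r = 0.07/0.30 = 23%.

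**Step 4: the same in whole numbers** (assumed), one arm of 175. Suppose 35 are symptomatic before treatment, 20 of them resolve, 5 of the remainder worsen, and 20 others develop symptoms.

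- Before: 35/175 = 20.0%
- After: (35 - 20 + 20)/175 = 20.0%
- 8.3 figure: 0.0 points
- Participants with an AE under 6.1.1: (20 + 5)/175 = 14.3%

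**The case against.** The netting depends on a reading. Taken literally, no AE exists before dosing, the 'before' proportion is zero, and the difference is simply the post-treatment AE proportion. That is possible, but it makes the word 'before' redundant, and the synopsis does call the pre-treatment interview an AE interview. The symptom reading is the likelier one, though it remains an inference.

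The loss of worsening is also conditional. Section 6.2 has unfavourable changes in a participant's condition recorded as AEs, so worsening would count if 'after' means those recorded AEs. Subtracting baseline symptoms would still not give the 6.1.1 proportion: with b = 30% in the example above, 10% - 30% = -20 points.

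The synopsis tables by group supply much of what is missing, and events are still graded and assessed one by one. This stands, and it limits the consequence. However, section 8.3 does not carry the tables over, and the synopsis does not say whether they count only new or worsened events.

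Randomisation balances baseline symptoms between arms in expectation. This helps a comparison of the two differences, but neither arm's proportion with a treatment-emergent AE is recovered.

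Three stronger inferences are not supported:

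- **That there is no baseline symptom information.** Section 4.3.3 and footnote (d) of Table 1 collect it.
- **That the choice of 'after' could move the result by some 20 points in practice.** With b = 30%, r = 25% lasting and 10% onset, counting any of five interviews gives 0.70 × (1 - 0.9^5) - 0.075 = +21.2 points if onsets are independent, against -0.5 if the same people report each time. The upper value is a mathematical bound on assumed inputs. Section 6.1 says few AEs have been reported with these drugs.
- **That the symptom lists before and after do not match in any important way.** Footnote (f) names allergic reaction and footnote (d) does not, but both end in an open item.

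**Conclusion.** The point holds in a limited form. On the most plausible reading, the 8.3 figure is new onset minus resolved baseline symptoms and does not estimate the proportion with an AE under section 6.1.1. Where baseline symptoms are common and often resolve, it can be near zero or negative despite real treatment-emergent events. Where they are uncommon it understates but stays positive in the illustration (+4.0 to +9.0 points against 10%). These sizes rest wholly on assumed rates.

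That 'after' is undefined, and that section 8.3 and the synopsis are not aligned, hold on any reading.

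The summary is secondary and descriptive, with no test or decision attached, and the primary analysis and sample size are unaffected. It should be corrected, but it does not threaten the trial's main conclusion. A reader might infer that the trial could not report treatment-emergent AEs at all. The documents do not support this: new-onset events can be derived from the planned interviews, and so can worsening where a pre-treatment grade is recorded.

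**What to change.** Replace the AE sentence in section 8.3 with wording such as:

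> For each post-treatment interview and overall, the number and proportion of participants in each arm with at least one AE that is new, or worse in grade, relative to the pre-treatment symptom interview will be reported and compared descriptively between arms. Pre-treatment symptom prevalence will be shown alongside.

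Use the same wording in the Statistical Analyses row of the synopsis. This also settles what 'after' means.

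As an optional addition, record a grade on the section 6.1.2 scale for symptoms found before treatment, so that worsening is easier to identify.

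The cost is a wording change in two places and a little analysis on interviews already planned. The optional grade needs at most one CRF field, if it is not already there.
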